1.2. Study Schema

Group 1 and Group 4: Dosing on Days -43 and -22, and -14.

Group 2 and Group 5: Dosing on Days -24 and -3.

Group 3 and Group 6: Dosing on Days -22 and -1.

Treatment areas of each subject group will be marked: Treatment Area 1 and Treatment Area 2.

By the end of the dosing phase:

- Treatment Area 1 will receive a total of 2 doses (referred to as multiple doses in the objectives) at specified study visits for the group assigned.
- Treatment Area 2 will receive a total of 1 dose (referred to as single dose in the objectives) at specified study visits for the group assigned.

1.3. Schedule of Activities

	Dosing Visit Groups 1 and 4: Day -43, Day -22 (±2 days)	Dosing Visit Groups 1 and 4: Day -14 (±2 days)	Dosing Visit Groups 2 and 5: Day -24 (±2 days)	Dosing Visit Groups 2 and 5: Day -3 (-2 days)	Surgery Visit All Groups: Day 0 (Day of Abdominoplasty)	All Groups: Day 7 Post-surgery follow-up visit (±3 day)	All Groups: Day 28 Post-surgery follow-up visit/ EOS/Early Termination visit (±3 days)
Screening Visit (28 days)							
Procedures							
Informed consent^a	X						
Inclusion/exclusion criteria review^{a,b}	X		X		X		
Medical history (including previous medications/ procedures/surgery/obstetrics)		X					
Prior/concomitant medications/procedures	X		X		X	X	X
Physical Examination	X				X ^c	X	X
Height, weight, BMI confirmation	X						
Vital signs	X		X ^d		X	X	X
Clinical laboratory testing^{b,e}	X				X ^f		
Anti-AUX-I/anti-AUX-II antibody level sample collection and processing^g	X					X ^l	X
Medical clearance for surgery	X					X	
Serum pregnancy testing	X ^h						
Urine pregnancy testing		X		X		X	X

	Dosing Visit Groups 1 and 4: Day -43, Day -22 (±2 days)	Dosing Visit Groups 1 and 4: Day -14 (±2 days)	Surgery Visit All Groups: Day -30 through Day -1 (-2 days)	All Groups: Day 28 Post-surgery follow-up visit/ EOS/Early Termination visit (±3 days)
Screening Visit (28 days)	Groups 2 and 5: Day -24 (±2 days)	Groups 2 and 5: Day -3 (-2 days)	All Groups: Day 0 (Day of Abdominoplasty)	
Procedures	Groups 3 and 6: Day -22 (±2 days)	Group 3 and 6: Day -1 (-1 day)		
Marking and labeling the site of injection (treatment and control) with surgical marker (Treatment Area 1, Non-injected/Control Area, and Treatment Area 2)	X	X	X	X
Digital Photography ⁱ	X	X	X	X
CCH injection (approximately 0.07 mg) at Area 1	X	X		
CCH injection (approximately 0.07 mg) at Area 2		X ^j		
Abdominoplasty procedure				X
Tissue excision and handling procedures for shipment				X
Injection site evaluation (ie, adverse reactions/local tolerability in treatment areas) ^k		X	X	X
All other adverse events	X			Monitored Throughout Study

Note: AUX-I = Clostridial class I collagenase, AUX-II = Clostridial class II collagenase, ECG = Electrocardiogram, EOS = End of Study

Note: Unless otherwise stated above or outlined below (and with the exception of injection site reactions/local tolerability in the area treated), all assessments should be completed **prior** to study treatment administration on Treatment Days.

^a Performed prior to any study-required assessments.

^b Laboratory safety testing will be performed at the investigative site or designated laboratory, as part of the standard of care (hematology, biochemistry, ECG, etc) of the subject's preparation for elective abdominoplasty as deemed required by the investigator. These testing results will be assessed for inclusion/exclusion

criteria by the investigator. All inclusion/exclusion criteria should be reassessed and verified **prior** to the first dose of study treatment. In the event that any safety laboratory testing results are unavailable prior to the subject's first dosing visit, the investigator will notify the sponsor to discuss on a case-by-case basis, prior to administering any study treatment to the subject.

- c Physical examination performed prior to surgery.
- d Vital signs (blood pressure, respiratory rate, pulse rate, and body temperature) will be collected up to **2 hours prior** to dosing, at **30 minutes after** dosing, and also at **15 minutes after dosing (without body temperature)** on Days -43, -24, -22, -14, -3, and -1 at dosing visits. **All vital sign measurements should be taken after the subject has been sitting for 5 minutes.** Vital signs **must be stable** before the subject is discharged.
- e Any clinical post-operative laboratory testing may be performed post-surgery through Day 28 as deemed necessary by the investigator.
- f Subjects in **Group 1 and Group 4** may undergo additional clinical laboratory safety testing as standard of care (hematology, biochemistry, ECG, etc) as part of additional preparation for abdominoplasty surgery (as well as any additional subjects, as deemed necessary, by the investigator).
- g Samples from Screening will be analyzed for anti-AUX-I and anti-AUX-II antibodies; samples from Day 0 and Day 28 Follow-up (EOS/Early Termination) visits will be analyzed for anti-AUX-I antibodies, anti-AUX-II antibodies, and neutralizing antibodies.
- h Serum pregnancy testing results must be reviewed by the investigator **prior** to the first dose of study treatment.
- i All photographs should be taken after marking the treatment and control areas with a surgical marker, but prior to CCH injection or abdominoplasty surgery. No manipulation of the treatment or control areas should be done prior to the photographs being taken.
- j Treatment Area 1 in Group 1 and Group 4 will receive the first treatment on Day -22 (Note: for Group 1 and Group 4, treatment on Day -14 will occur in Treatment Area 2 NOT in Treatment Area 1). (Please see **Study Schema Section 1.2**).
- k Local AEs associated with the injection site, including acute (eg, erythema, bruising, pain, nodules/mass, ulceration, blistering, pruritus, swelling, and/or induration) and/or chronic (eg, skin thickening, fibrosclerosis, and peau d'orange changes) cutaneous AEs, will be recorded and evaluated for seriousness and severity.
- l Day 0 samples for anti-AUX-I, anti-AUX-II, and neutralizing antibodies may be collected as part of the standard of care presurgical visit that is nearest to the scheduled date of the abdominoplasty procedure (after dosing visits are completed).

2.2. Introduction to Study

CCH is a parenteral lyophilized product comprised of 2 collagenases in an approximate 1:1 mass ratio, Collagenase I (Clostridial class I collagenase [AUX-I]) and Collagenase II (Clostridial class II collagenase [AUX-II]). CCH is a novel formulation of an existing product (XIAFLEX®) that is currently approved for use in adults with Dupuytren's contracture and Peyronie's disease.

2.3. Study Rationale

CCH dose administration in buttocks or thighs with cellulite has shown to deliver an aesthetic improvement in the treated area. Endo studied the safety and efficacy of CCH 0.84 mg dose per treatment area (1 buttock or 1 thigh) in multiple Phase 2 and Phase 3 studies. In these studies, up to 12 cellulite dimples per treatment area (1 buttock or 1 thigh) were injected in each subject in 1 treatment session, and the approximate dose per dimple was 0.07 mg CCH. The efficacy results from these studies, based on improvement in cellulite severity as determined by the investigator and the subject, have consistently shown that CCH 0.84 mg dose per treatment area is an effective treatment for cellulite in buttocks or thighs. In addition, the safety and immunogenicity profile of CCH has been consistent across all these studies.

The majority of adverse events (AEs) occurred at the site of injection and resolved before the next scheduled treatment in these studies. Among the injection site reactions observed across these studies, the most common was injection site bruising. Injection site bruising observed in the clinical studies was self-limiting and predominately mild-to-moderate in severity. However, there was no histopathology examination of the injection site bruise area.

Tissue samples isolated from subjects undergoing an elective abdominoplasty procedure offer an opportunity to observe histopathological structure changes of tissues post treatment with CCH.

The histostain or microscopic examination of biological tissues may reveal the appearance of tissues in greater detail and bring better understanding of CCH treatment effect on tissue structure.

This study (EN3835-213) is an exploratory investigation to learn and compare the histopathology and immunohistochemistry changes, if any, in the subcutaneous tissue and surrounding area after single and multiple CCH injections of the abdomen across different time points. The abdominal area injected with CCH will be within the area targeted for excision during abdominoplasty.

2.4. Background

2.4.1. Product Background

EN3835 is a parenteral lyophilized product comprised of 2 collagenases in an approximate 1:1 mass ratio (AUX-I and AUX-II). EN3835, marketed as XIAFLEX®, is currently approved for use in adults with Dupuytren's contracture and Peyronie's disease. These collagenases are proteinases that hydrolyze collagen in its native triple helical conformation under physiological conditions, resulting in lysis of collagen deposits in a Dupuytren's cord and/or Peyronie's plaque.

To investigate EN3835 in the treatment of edematous fibrosclerotic panniculopathy (EFP), commonly known as cellulite, Endo Pharmaceuticals Inc. (Endo) has developed a novel formulation of EN3835, referred to hereafter as CCH, with a different concentration and volume than the approved EN3835 formulation.

Cellulite is an aesthetic condition that can be understood as an imbalance between the structural characteristics and biomechanical properties (ie, the delicate containment and extrusion forces) at the subdermal junction (Rudolph et al, 2019). As such, the goals of cellulite treatment are to strengthen the subdermal interface and/or to release the fibrous septae via various types of subcision (Rudolph et al, 2019). The fibrous septae has been recognized as a contributory underlying cause of cellulite and as a target of treatment for cellulite by anatomical and image analyses studies (Hexsel et al, 2009; Hexsel et al 2016; Mirrashed et al, 2004; Nürnberg and Müller, 1978; Piérard et al, 2000; Querleux et al, 2002).

A number of therapies have been utilized in an attempt to treat cellulite, much of the evidence for their efficacy is anecdotal, subjective, or based only on patient self-assessment and many of the treatments have undesirable side effects (Avram, 2004; Collis et al, 1999; Khan et al, 2010; Hexsel and Mazzuco, 2000). Some of the historical treatments for EFP have included weight loss, pharmacological agents (eg, xanthines, retinoids, lactic acid, and herbals), Endermologie® or lipomassage, mesotherapy, radiofrequency, subcision (including powered subcision eg, Cellfina®), and laser (including Triactive® and CelluLaze™) (Boyce et al, 2005; DiBernardo, 2011; Hexsel and Mazzuco, 2000; Khan et al, 2010). However, there remains an unmet need for safe and effective nonsurgical therapies to improve the aesthetic outcome in women with cellulite. CCH has the potential to effectively lyse the subdermally located fibrous septae, the underlying cause of the skin dimpling in women with cellulite, at the site of injection.

The results from previous studies have shown improvement in the severity of cellulite, as determined by both the investigator and the subject, in subjects treated with CCH administered at a dose of 0.84 mg per treatment area (1 buttock or 1 thigh) every 21 days for 3 sessions. Across

[figure not shown]
all previous studies, CCH has demonstrated an acceptable safety and immunogenicity profile. The majority of AEs occurred at the site of injection, were mild to moderate in nature, and often resolved within 2 to 3 weeks without any sequelae.

A detailed description of the chemistry, pharmacology, efficacy, and safety of CCH is provided in the Investigational Brochure (IB) (Endo, 2019).

2.4.2. Medical Procedure Background

The origins of abdominal and body contouring procedures emanate from the earliest awareness of self. In the late 1800s, abdominal wall surgeries were performed to address disfigurements and deformities of skin, fat, and the musculofascial system, which were attributed to scars, injuries, or defects. However, the modern history of abdominoplasty can be traced to the late 1960s and 1970s when it was accepted as an aesthetic procedure commonly performed to eliminate excess skin and fat accumulation in the abdominal area (Matarasso, 1991).

Suction-assisted lipectomy was developed in the 1980s, and subsequently a collective group of abdomen contour procedures, referred as abdominolipoplasty, which combined the liposuction with modifications in traditional abdominoplasty techniques became available. In 1989, Matarasso came up with general guideline to organize an approach to abdominolipoplasty surgeries based on the evaluation of skin, fat and, the musculofascial system (diagrammed in Figure 1). In 2018, more than 130,000 abdominoplasty procedures were performed in the United States, making abdominoplasty among the top 5 cosmetic surgery procedures in the United States. Compared to the approximately 62,000 procedures performed in 2000, abdominoplasty has increased in popularity by 107 percent (ASPS, 2019).

Figure 1: The Abdominolipoplasty System of Classification and Treatment

Abbreviations: SAL, suction-assisted lipectomy.

Pink arrows = liposuction; yellow = undermining; green = excision; cross-hatching = fascial plication.

Matarasso, 2010.

2.5. Risk/Benefit Assessment

Current treatments for EFP have limited efficacy and undesirable side effects. There remains an unmet need for safe and effective nonsurgical therapies to improve the aesthetic outcome in women with cellulite.

The following AEs have been commonly observed in subjects treated with CCH for EFP: local injection site reactions including injection site bruising, injection site swelling, and injection site pain. These events are similar to events reported in the clinical trials of EN3835 for the approved indications. Postmarketing safety data are consistent with safety data reported in clinical trials. AEs reported to date in the completed Phase 3 trials of CCH for the treatment of EFP in the buttocks have been consistent with previously reported AEs in the studies to date.

More detailed information about the known and expected benefit, risks, and reasonably expected AEs can be found in the IB (Endo, 2019).

All procedures and activities in this study (except for CCH study drug administration, digital photography, and immunogenicity testing) are generally accepted as standard-of-care for patients undergoing abdominoplasty and do not present any increased risk to the subjects.

3. OBJECTIVES AND ENDPOINTS

Objectives	Endpoints

Primary
 
 To evaluate the histopathology and immunohistochemistry of subcutaneous tissue isolated after single and multiple CCH doses with both a [REDACTED] single injection technique and [REDACTED] (relative to control, non-dosed tissue) in adult female subjects undergoing abdominoplasty. 	
 The primary endpoint will be the change in histopathology and immunohistochemistry of tissue dosed with CCH relative to control tissue (tissue not dosed with CCH). 
 ○ [REDACTED] single injection technique: 
 ▪ Area 1 tissue relative to control for all groups. ▪ Area 2 tissue relative to control for all groups. ○ [REDACTED] 
 ▪ Area 1 tissue relative to control for all groups. ▪ Area 2 tissue relative to control for all groups.

Secondary
 
 To compare the histopathology and immunohistochemistry of tissue from treatment areas dosed with CCH in adult women undergoing elective abdominoplasty surgery. 
 ○ Multiple doses versus single dose with a [REDACTED] single injection technique. 	
 The change in histopathology and immunohistochemistry of tissue samples dosed with CCH multiple times relative to tissues dosed with CCH a single time with a [REDACTED] injection technique. 
 ○ Area 1 tissues relative to Area 2 for all groups.


 ○ Multiple doses versus single dose with a [REDACTED] [REDACTED] ○ Multiple doses with a [REDACTED] versus multiple dose with a single injection technique. ○ Single dosing with a [REDACTED] versus single dosing with a [REDACTED] single injection technique. 	
 ● The change in histopathology and immunohistochemistry of tissue samples dosed with CCH multiple times relative to tissue dosed with CCH a single time with a [REDACTED] injection technique. 
 ○ Area 1 tissues relative to Area 2 for all groups. ● The change in histopathology and immunohistochemistry of tissue samples dosed with CCH multiple times with a [REDACTED] single injection technique relative to tissues dosed with CCH multiple times with a [REDACTED] technique. ● The change in histopathology and immunohistochemistry of tissue samples dosed with CCH a single time with a [REDACTED] single injection technique relative to tissues dosed with CCH a single time with a [REDACTED] technique.

 ● To assess the safety and immunogenicity of CCH injected in adult women undergoing an elective abdominoplasty surgery. 	
 ● Treatment-emergent adverse events (TEAEs). ● Adverse events of special interest (AESI). ● Anti-AUX-I antibodies, anti-AUX-II antibodies, and neutralizing antibodies analysis.

The primary objective will be met if histopathology and immunohistochemistry findings in the excised abdominal tissues dosed with CCH demonstrate change from histopathology and immunohistochemistry findings in non-dosed control tissue.

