Subjects in each group will receive up to 3 CCH doses (each dose as either a [REDACTED] single injection technique or a [REDACTED] across 2 treatment areas at the following dosing visits:

Group 1 and Group 4 (n = 2 subjects/group): Dosing on Days -43 and -22, and -14.

Group 2 and Group 5 (n = 1 subject/group): Dosing on Days -24 and -3.

Group 3 and Group 6 (n = 1 subject/group): Dosing on Days -22 and -1.

At each dosing visit, the CCH injection dose administered per treatment area (Area 1 or Area 2) is approximately 0.07 mg CCH/0.3 mL (administered subcutaneously as 3 aliquots of [REDACTED] mL each in a single injection technique in Group 1, Group 2, and Group 3) or approximately 0.07 mg CCH/1.5 mL (administered subcutaneously as [REDACTED] of approximately [REDACTED] mL each in a [REDACTED] in Group 4, Group 5, and Group 6). Following administration of 3 doses of CCH, abdominoplasty and collection of the excised abdominal tissue will occur on Day 0. Subjects will be followed for safety until 28 days post-surgery.

The duration of the study from first subject first visit to last subject last visit will be dependent on the ability of the investigative sites to identify and enroll eligible 10 subjects. Total study duration for each subject is approximately 50 to 71 days depending on the group assigned (not including the screening period of up to 28 days). With the addition of 2 replacement subjects due

to COVID-19, the approximate duration of the study has been increased and is to be determined due to COVID-19 impacts.

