6.4. Measures to Minimize Bias

This is an open label, nonrandomized study. The pathologist, who is blinded to the dosing schedule, will report any observed tissue differences from the control area (not injected).

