9.3. Statistical Hypotheses and Analyses

No statistical hypotheses and analyses are planned for the study. Subject narratives will be developed based on the histopathology and immunohistochemistry reports and safety data listings.

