9.3.1. Histopathology and Immunohistochemistry

Histopathology and immunohistochemistry findings in the excised abdominal tissues injected with CCH will be compared to histopathology and immunohistochemistry findings in non-injected control tissue. Also, histopathology and immunohistochemistry findings in the excised abdominal tissues dosed twice with CCH will be compared to histopathology and immunohistochemistry findings in excised abdominal tissues dosed only once with CCH.

The pathologist, blind to the dosing schedule, will report any observed tissue differences from the control area (not injected).

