3.7. Gross Pathology, Histopathology, and Immunohistochemistry

Digital photography will be conducted so that the photographs of the treatment area can assist the histopathologist/evaluator in assessing the gross pathology and histopathology of the excised tissues.

The subjects will be photographed after marking the treatment areas and the injection sites with a surgical marker (but prior to CCH injection) at each dosing visit, while the subject is in a consistent, standardized relaxed standing pose.

At Day 0 (Day of Surgery), the treatment areas will be again photographed after marking the treatment area but prior to the abdominoplasty procedure, while the subject is in a consistent, standardized relaxed standing pose.

No manipulation of the treatment or control areas should be done prior to the photographs being taken.

Histopathology and immunohistochemistry of the excised abdominal tissue will be performed at the central pathology laboratory.

Histopathology and immunohistochemistry findings in the excised abdominal tissues injected with CCH will be compared to histopathology and immunohistochemistry findings in noninjected control tissue. Comparisons will also be made between tissues dosed twice with CCH versus tissue dosed only once, and tissue dosed using the [REDACTED] technique versus the [REDACTED].

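### In Groups 1 and 4 the Area 1 versus Area 2 comparison mixes number of doses with time since the last injection; separately, protocol footnote j conflicts with the two-dose Area 1 schedule

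*Protocol*

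**What the plan says.** Protocol Section 3 lists, for each of the two injection techniques, a secondary endpoint comparing tissue dosed several times with tissue dosed once. Both are operationalised as "Area 1 tissues relative to Area 2 for all groups". Protocol Section 9.3.1 restates the comparison: findings in "excised abdominal tissues dosed twice with CCH will be compared to histopathology and immunohistochemistry findings in excised abdominal tissues dosed only once". SAP Section 3.7 does the same: "Comparisons will also be made between tissues dosed twice with CCH versus tissue dosed only once". None of these places mentions time since injection.

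The schedule in Protocol Section 4.1 is "Group 1 and Group 4 (n = 2 subjects/group): Dosing on Days -43 and -22, and -14", with excision on Day 0. Footnote j to the schedule of activities, in the protocol and in the SAP, assigns Day -14 to Area 2 and not to Area 1.

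Varied timing is intended. Protocol Section 2.3 describes studying changes "after single and multiple CCH injections of the abdomen across different time points". On reporting, Protocol Section 9.3 plans no hypotheses: "Subject narratives will be developed based on the histopathology and immunohistochemistry reports and safety data listings".

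On the separate item, Protocol Sections 1.2 and 4.1 and Table 1 give Area 1 two doses in every group. Protocol footnote j places the first Area 1 treatment in Groups 1 and 4 on Day -22. SAP footnote j places the first on Day -43 and the second on Day -22.

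**The concern.** The endpoint labels an Area 1 versus Area 2 difference as an effect of repeat dosing. That label is clean only if the two areas differ in nothing else that matters. In Groups 1 and 4 they also differ in how long before excision they were last injected. A difference could come from the second dose, from the age of the injection, or from both; an absence of difference could be the two offsetting each other.

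The sponsor itself treats time since last dose as relevant to the tissue data. Protocol Section 2.1 sets a limit of 45 days from last dose to surgery and has two subjects who could not meet it replaced for endpoint purposes. Their histopathology is analysed separately. No comparable care is taken over the interval within a subject, between areas.

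At stake is the wording of one secondary, descriptive conclusion. The footnote conflict is a different matter: it concerns what the schedule of activities tells a site to do, and how Groups 1 and 4 are described in the report.

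**Working it through.** **Inputs.** Dosing days and group sizes: Protocol Section 4.1. Visit windows: Protocol Section 1.3, ±2 days for Days -43, -22 and -14. Area assignment of Day -14: footnote j in both documents. Surgery limit: Protocol Section 2.1, 45 days from last dose. Doses by area: Protocol Table 1.

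**Step 1: check the day numbering against the plan's own figures.** Duration per subject = 28 minus the first dosing day.
- Groups 1/4: 28 + 43 = 71
- Groups 2/5: 28 + 24 = 52
- Groups 3/6: 28 + 22 = 50

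This reproduces the stated 50 to 71 days. Planned subjects: 2 + 1 + 1 + 2 + 1 + 1 = 8, as stated.

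**Step 2: age of the last injection at excision, Groups 1/4.** Age = 0 minus the last dosing day of that area.

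| | Nominal | Within visit windows |
|---|---|---|
| Area 1 (Day -22) | 22 days | 20 to 24 |
| Area 2 (Day -14) | 14 days | 12 to 16 |
| Gap | 22 - 14 = 8 | 20 - 16 = 4 to 24 - 12 = 12 |

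The result is the same under either version of footnote j, because both make Day -22 the last Area 1 injection.

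**Step 3: later surgery.** The gap depends on dosing dates, not on the surgery date. At 45 days from the last dose, Area 2 is 45 days old and Area 1 is 45 + 8 = 53 days old. The ages move; the gap does not.

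**Step 4: the other groups.** They have two dosing visits and three doses, so Area 1 is dosed at both visits and Area 2 at one. If Area 2 is dosed at the later visit, as the schedule of activities appears to show, the ages match: 3 versus 3 days (Groups 2/5) and 1 versus 1 day (Groups 3/6). If it were the earlier visit, the gap would be 24 - 3 = 21 or 22 - 1 = 21 days. The table is broken and the schema is missing in the text reviewed, so this needs confirming.

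**Step 5: reach.** Groups 1 and 4 hold 2 + 2 = 4 of 8 planned subjects, or 2 of 4 within each technique. Protocol Section 9.1 gives group sizes as minimums, and the groups of the delayed and replacement subjects are not stated. The between-technique comparisons (Group 1 with 4, 2 with 5, 3 with 6) are matched on nominal age and are not affected.

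**Step 6: can timing enter the comparison as planned?** SAP Table 5 defines Study Day as assessment date minus surgery date, so for a dose it is the injection age with a minus sign. SAP Sections 7.9.1 and 7.6 list dose and surgery dates, and Section 6.1 lists all case report form data. The raw material is largely there. But Protocol Section 6.4 says: "The pathologist, who is blinded to the dosing schedule, will report any observed tissue differences from the control area". Timing can therefore enter only when the narratives are written, and no passage requires that.

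**Step 7: footnote j.** Read literally, the protocol version leaves Area 1 in Groups 1/4 with one dose and gives Day -43 no area.
- Group 1: 1 × 0.07 = 0.07 mg, against 2 × 0.07 = 0.14 mg in Table 1
- Group 4: 1 × 0.0653 = 0.0653 mg, against 2 × 0.0653 = 0.1306 mg, shown as 0.13 mg in Table 1

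**The case against.** The strongest reply is that nothing here is pooled or tested. The endpoint's reference to all groups can mean simply that the comparison is made in each group. With 1 or 2 subjects per group and subject narratives, the schedules are kept apart anyway. Timing varies by design, and matching on the last injection, rather than the first, is a choice the documents do not make. Listing shells are in SAP Module 2 and tissue handling is in the Histopathology Manual; neither was available, and the exposure listing may already carry the treatment area.

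Much of this stands. No pooled estimate is planned, so presenting results by schedule adds only a little to the narratives, and Protocol Section 3 need not be amended for this. What does not follow is that intended variation in timing turns the Groups 1/4 contrast into a dose-number effect, or that narratives will raise the matter unprompted.

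Three stronger readings are tempting but unsupported:
- Protocol Section 2.4.1 says that adverse events in previous studies "often resolved within 2 to 3 weeks without any sequelae". A reader might infer that Area 2 is sampled during a reaction and Area 1 after it. That passage concerns clinical events, not histology. The nominal 22 days is one day past three weeks, with a window of 20 to 24 straddling that limit, and actual surgery may be much later.
- A reader might infer that the primary objective is undermined. It rests on dosed versus undosed tissue, not on Area 1 versus Area 2.
- From footnote j a reader might infer that subjects were misdosed, or that Area 2 became the twice-dosed area. The documents do not report doses actually given by area, and no passage assigns Day -43 to Area 2. The wording may be a slip or text lost in extraction.

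**Conclusion.** Both items hold, within limits.

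**Comparison.** In Groups 1 and 4, nominally half the planned subjects, Area 1 versus Area 2 differs in dose number and also by 8 days in the age of the last injection (4 to 12 within windows). The contrast cannot by itself be credited to multiple dosing. The size and direction of any distortion are unknown, and the consequence is confined to interpreting a descriptive secondary comparison. This rests on the nominal schedule, the planned group sizes, and the absence of an injection-age rule in the two documents; unseen manuals or shells could supply part of it.

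**Footnote.** As supplied, protocol footnote j contradicts Protocol Sections 1.2 and 4.1, Table 1 and SAP footnote j. By Amendment 4 all 8 subjects then enrolled had finished dosing (Protocol Section 2.1), so the remaining reach is the 2 replacement subjects and the reporting of Groups 1 and 4. The comparison issue does not depend on it. No view is taken on which schedule is right.

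**What to change.** For the comparison, act in SAP Sections 3.7 and 7.9.1 and in the narratives:
- Keep all groups and present Area 1 versus Area 2 by dosing schedule (Groups 1/4, 2/5, 3/6).
- In the exposure listing, show treatment area and Study Day for each dose.
- In each narrative, give the actual days from last dose to excision for each area.
- State that Groups 1 and 4 reflect dose number and injection age together and cannot alone support a multiple-versus-single conclusion.
- Confirm against the schema at which visit Area 2 is dosed in Groups 2, 3, 5 and 6.

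The cost is wording and one label in an existing listing. No new derived variable is needed; no new data are needed if the case report form records treatment area per injection, which the documents do not state outright. The price is that a dose-number reading then rests mainly on about 4 subjects, and only if the schema confirms matched timing.

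For footnote j, check the source document for lost text. If the wording stands, reconcile it with Protocol Sections 1.2 and 4.1, Section 6.2 with Table 1, and SAP footnote j. A change to the protocol would need ethics approval and the investigator's signed page under Protocol Section 10.1.1.
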